3.8.8.6 Pain Crisis Events

Sickle cell-related pain crisis events will be documented throughout the duration of the trial. Each crisis will be reported to the Sponsor within 24 hours of the Investigator becoming aware of the event.

An on-study sickle cell-related pain crisis is defined as an acute episode of new-onset pain that lasts at least 2 hours with no medically determined cause other than a vaso-occlusive event and that requires treatment with oral or parenteral opioids, or parenteral nonsteroidal anti-inflammatory drugs, or other analgesics prescribed by a healthcare provider in a medical facility or by telephone management documented in medical records. Note that this definition differs slightly from the definition that is to be used to assess study eligibility (see Inclusion #6).

Acute chest syndrome, hepatic sequestration, splenic sequestration, priapism (each requiring a visit to a medical facility or documented telephone management) and death (except that due to suicide, accident, or other event clearly unrelated to the patient's medical condition) will also be considered pain crises, as well as subtypes of pain crises, for analysis purposes.

In the event of a sickle cell-related pain crisis, the following laboratory values, at minimum, should be recorded if part of local practice and available to the study site: hemoglobin, reticulocyte count (% and absolute), C-reactive protein, direct and indirect bilirubin, lactic dehydrogenase, and haptoglobin.

Information regarding the TEAEs related to the underlying disease will remain part of the Sponsor's ongoing internal signal detection process. To ensure consistency, all crisis events will be reviewed by the CEAC (see Section 5.13). Because these events are anticipated in this study population, the Sponsor does not anticipate reporting them as IND safety reports unless evidence suggests a causal relationship between the drug and the events.

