### 3. Study Objectives

#### 3.1. Study Objectives and Endpoints

Table 1 provides the study objectives and the corresponding endpoint(s) that will be summarized and analyzed to determine if the objective is met.

Table 1: Study objectives and corresponding endpoints

Objective	Endpoint
	Primary
The primary objective is to assess the safety and tolerability of oral, once-daily (QD) olinciguat when administered for approximately 12 weeks to participants aged 16 to 70 years with sickle cell disease (SCD).	Incidence (number and percentage of patients) and frequency (number of events) of treatment-emergent adverse events (TEAEs) Incidence of TEAEs by severity Incidence of study drug-related TEAEs
Exploratory Patient-reported Outcomes	
To evaluate the effect of oral, once-daily olinciguat on symptoms of SCD, health-related quality of life, and biomarkers when administered for approximately 12 weeks to participants aged 16 to 70 years with SCD	Change from baseline in Sickle Cell Disease – Symptom Assessment Form (SCD-SAF) total score at Weeks 4, 8, 12, and End of Treatment (EOT) Pain as measured on the 11-point numerical rating scale (NRS) by week and for the overall Treatment Period Percent change from baseline in pain as measured on the 11-point NRS by week and for the overall Treatment Period Change from baseline in pain as measured on the 11-point NRS by week and for the overall Treatment Period Change from baseline in fatigue as measured on the 11-point NRS by week and for the overall Treatment Period Change from baseline ASCQ-Me pain impact score
Exploratory Pharmacodynamics	
To evaluate the effect of oral, once-daily olinciguat on symptoms of SCD, health-related quality of life, and biomarkers when administered for approximately 12 weeks to participants aged 16 to 70 years with SCD	Change from baseline in hemoglobin at Weeks 4, 8 and 12 Proportion of patients with change from baseline in hemoglobin $\geq 1$ g/dL at end of treatment Change from baseline in fetal hemoglobin at Weeks 4, 8 and 12
Exploratory Pharmacokinetics	
To evaluate the pharmacokinetics (PK) of oral, once-daily olinciguat when administered for approximately 12 weeks to participants aged 16 to 70 with SCD	Plasma concentrations of olinciguat at assessed timepoints

Note: Bolded parameters associate directly with corresponding endpoint(s).

This document is confidential.

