### 5.2.4. TEAE, SAE, On-therapy SAE

TEAEs are defined as AEs with a reported started date/time that is on/after the first dose date/time the participant receives randomized treatment through 7 days after the last dose of study medication.

SAEs are AEs that result in death, are life-threatening, require hospitalization or prolongation of existing hospitalization, are persistent or result in significant disability/incapacity, result in a congenital anomaly/birth defect, or are important medical events (eg, events that may not result in death, are life threatening, or require hospitalization; such events may be considered serious when, based on appropriate medical judgment, it may jeopardize the participant and may require medical or surgical intervention to prevent 1 of the outcomes listed in the wider SAE definition).

On-therapy SAEs are those SAEs that start after the participant has received the first dose of randomized study drug and through 28 days after the final study drug dose.

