### 7.2. Adverse Events

AEs will be coded using the MedDRA Version 20.0 or later and will be classified by MedDRA SOC and PT.

AEs are collected from date of signed informed consent form (ICF) through the last Follow-up Visit. TEAEs, SAEs, and on-therapy SAEs are defined in [Section 5.2.4](#). Pre-treatment AEs during Screening are defined as AEs started on/after Screening Visit and before the first dose of Run-in placebo. Pre-treatment AEs during Single-blind Run-in Period are defined as AEs started on/after the first dose of Run-in placebo and before the first dose of randomized study drug.

The number and percentage of participants who experience at least 1 TEAE as well as those who experience each specific SOC and PT will be presented by treatment group for the Safety Population. For presentation of AE incidence, AEs will be sorted by SOC, and within each SOC, by PT in the decreasing incidence of the last column of summary table, and then the column before it one by one. AEs will also be presented by severity (CTCAE v.4.03; Grade 1–Grade 5). For AEs that change severity ratings, the AE will be included only once in the summaries, under the maximum severity rating assigned by the Investigator. Additionally, TEAEs and SAEs occurring in the first, second, and fifth week of the double-

This document is confidential.

blind Treatment Period will be listed separately to distinguish among any effects of the initial dose (Week 1), the up-titrated dose (Week 2), and the further up-titrated dose (Week 5).

AEs occurring during Screening and the Single-blind Run-in Period will be summarized and listed separately.

More specifically, the following summary tables will be provided:

1. Overall Summary of TEAEs
2. Incidence of TEAEs by SOC and PT
3. Incidence of TEAEs by SOC, PT, and severity
4. Incidence of TEAEs by SOC, PT and relationship to double-blind study drug
5. Incidence of on-therapy SAEs by PT
6. Incidence of AEs leading to study drug discontinuation by PT
7. Incidence of pre-treatment AEs during Screening by SOC and PT (Screened Population)
8. Incidence of pre-treatment AEs during Single-blind Run-in Period by SOC and PT (Single-blind Run-in Population)
9. Incidence of adverse events of special interest (AESIs) by PT
10. Incidence of TEAEs by SOC, PT, and region (US vs. Lebanon)
11. Incidence of VOCs by PT
12. Summary of VOC events by location (eg, extremity) and outcome (eg, acute chest syndrome)

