### 8.2. Vaso-occlusive Crisis (VOC)

#### 8.2.1. Primary Analysis of Exploratory VOC Parameters

Sickle cell-related pain crisis events will be documented as 'vaso-occlusive crises' (VOCs) on the AE eCRF page throughout the duration of the trial and adjudicated by an independent adjudicator. Only

This document is confidential.

adjudicated events that are deemed VOCs will be utilized in the endpoints defined below. An on-study sickle cell-related VOC is defined in [Section 5.2.5](#).

Acute chest syndrome, hepatic sequestration, splenic sequestration, priapism (each requiring a visit to a medical facility or documented telephone management) and death (except that due to suicide, accident, or other event clearly unrelated to the participant's medical condition) will also be considered VOCs, as well as subtypes of VOCs, for analysis purposes.

The exploratory VOC parameters are listed here:

- Time to first VOCs experienced during the Treatment Period, defined as (start date of VOC – the date of first dose of double-blind study drug + 1)
- Proportion of participants experiencing  $\geq 1$  VOC during the Treatment Period
- Annualized VOC rate during the Treatment Period, defined as  $365^*$  total number of events/ (last dose date – first dose date of double-blind study drug +1)

All 3 VOC parameters will be summarized by descriptive statistics by treatment group.

The time to first VOC will be summarized using Kaplan Meier method; the median event time (if appropriate) and 2-sided 95% CI for the median will be provided; 25% and 75% percentiles will also be presented. Additionally, the Kaplan Meier plots will be generated. For comparison between each olinciguat group and the corresponding placebo group, P-value will be generated from log-rank test.

Example SAS code for Kaplan Meier method is shown below:

```
Proc lifetest data=analysis_data;
  Time AVAL*CNSR(1);
  Strata trt;
Run;
```

For the proportion of participants experiencing  $\geq 1$  VOC (dichotomous endpoint), the proportions for each olinciguat treatment group and the corresponding placebo group will be compared using a Cochran-Mantel-Haenszel (CMH) test controlling for stratification factors (HU use). The difference in the proportions between each olinciguat group and the placebo group as well as the CMH estimates of odds ratio, risk difference, and p-values will be presented, along with the corresponding 2-sided 95% CIs.

Example SAS code for CMH model is listed as below:

```

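### Vaso-occlusive crises count as TEAEs, and no planned table shows how many patients had a TEAE, a Grade ≥3 TEAE or an SAE other than a crisis

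*SAP*

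**What the plan says.** - **Recording.** SAP 8.2.1: "Sickle cell-related pain crisis events will be documented as 'vaso-occlusive crises' (VOCs) on the AE eCRF page throughout the duration of the trial".
- **Definition.** SAP 5.2.4: "TEAEs are defined as AEs with a reported started date/time that is on/after the first dose date/time the participant receives randomized treatment". The window closes 7 days after the final dose. Nothing is carved out for events of the underlying disease. Protocol 3.8.8.6, on pain crises, itself uses the term, in a sentence about internal signal detection that begins "Information regarding the TEAEs related to the underlying disease will remain part of". It explains the expedited-reporting position with "Because these events are anticipated in this study population".
- **Primary endpoint.** SAP 3.1, Table 1 lists the incidence and number of TEAEs, "Incidence of TEAEs by severity", and the incidence of drug-related TEAEs. Protocol 4.1.1 frames these as a comparison with placebo. SAEs are not in that list. They have their own table in SAP 7.2, with a window that runs to 28 days after the last dose (SAP 5.2.4).
- **Tables.** For each treatment group, SAP 7.2 plans "The number and percentage of participants who experience at least 1 TEAE as well as those who experience each specific SOC and PT". It names 12 summary tables. They include an overall TEAE summary, TEAEs by SOC and PT, by severity and by relationship, on-therapy SAEs by PT, AESIs by PT, and two VOC tables (items 11 and 12). None is described as leaving crises out.
- **Response measure.** SAP 8.2.1 also analyses adjudicated VOCs as time to first event, proportion with an event, and annualized rate.

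**The concern.** One type of event sits on both sides of the trial: in the harm count that serves the primary objective, and in the exploratory evidence of benefit. Crises should be frequent. Inclusion criterion 6 requires 1 to 10 in the year before screening. The on-study definition is also wider than the entry definition, because it accepts documented telephone management where entry requires attendance at a facility.

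A patient who has a crisis is already counted as having a TEAE, so a drug-caused event in that patient adds nothing to the any-TEAE row. If the drug also prevents crises, the fall in crises is subtracted from any rise in other events. The row could then show little difference, or favour the drug, when non-crisis events are more common on treatment. What is at stake is how the aggregate tolerability rates read against placebo.

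**Working it through.** **Plan figures.** The documents give no expected TEAE, SAE or VOC rate, so there is none to reproduce. The sample size was set outside statistical considerations. The planned counts agree: 40 + 48 = 88. Under Amendment 4 and later, 48 at 3:1 gives 36 on 18 mg and 12 on placebo.

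**Inputs from the documents.** Crisis history of 1 to 10 a year (inclusion criterion 6). TEAE window to 7 days after the last dose: with Day 85 as last dose, (85 + 7)/365.25 = 0.252 years. SAE window: (85 + 28)/365.25 = 0.309 years.

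**Assumptions.** The past rate continues as a Poisson process. Crises and other events are independent. Illustrative non-crisis TEAE risks are 40% on placebo and 60% on drug, a true difference of 20 points.

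**Formulas.**
- P(at least 1 VOC) = 1 − exp(−rate × window).
- P(any TEAE) = 1 − (1 − p_nonVOC)(1 − p_VOC).
- With the same p_VOC in both arms, the any-TEAE difference is the non-crisis difference times (1 − p_VOC).

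| Crises per year | P(≥1 VOC) | Share of difference left | Any-TEAE difference, no VOC effect | VOC rate cut 30% | VOC rate cut 50% |
|---|---|---|---|---|---|
| 1 | 22% | 78% | +15.5 | +13.1 | +11.4 |
| 3 | 53% | 47% | +9.4 | +4.6 | +0.8 |
| 5 | 72% | 28% | +5.7 | +0.5 | −4.3 |
| 10 | 92% | 8% | +1.6 | −2.0 | −6.5 |

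Differences are in percentage points, against +20 with crises left out. Example at 3 a year: p_VOC = 1 − exp(−3 × 0.252) = 0.530. Placebo is 1 − 0.60 × 0.470 = 0.718 and drug is 1 − 0.40 × 0.470 = 0.812, a difference of 9.4 points.

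**Event counts.** The shrinkage applies to patient-level risks. For the frequency component, crises unaffected by drug add the same mean number to each arm: 3 × 0.252 = 0.76 per patient at 3 a year. The absolute difference in mean events is unchanged, but the ratio moves towards 1. A 30% cut in crises would subtract 0.3 × 0.76 = 0.23 events per patient from the drug arm.

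**SAEs.** Assume non-crisis SAE risks of 5% and 15%, and 30% of crises hospitalized. At 3 crises a year, P(≥1 hospitalized VOC) = 1 − exp(−3 × 0.3 × 0.309) = 0.243. The any-SAE difference is +7.6 points with no VOC effect, +2.0 with a 30% cut and −2.0 with a 50% cut, against +10 with crises left out.

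**Can the missing count be rebuilt from the planned tables?** No. The VOC tables count patients with a crisis, and the PT tables count patients per term. A patient may appear under several terms and may have both kinds of event, so PT rows do not add up to patients with at least 1 non-crisis event.

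**The case against.** The case against is substantial, and most of it narrows the point.

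- **The primary endpoint has a component that already filters disease events.** Drug-related TEAEs are listed in both documents. This stands, although the filter is the investigator's judgement of causality.
- **Specific harms stay visible.** The SOC/PT, severity, relationship, discontinuation and AESI tables, the two VOC tables and the separate listings let a reader see hypotension, bleeding or any other term directly. This stands. A reader might infer that the plan hides drug harms. It does not: only the aggregate patient-level rows are diluted.
- **No decision hangs on those rows.** Safety is descriptive, with no test or margin. With 36 and 12 patients and the 60% and 40% used above, the 95% half-width is 1.96 × √(0.24/36 + 0.24/12) = 32 points, wider than any shift in the table. This stands as a limit on importance. It does not remove a systematic dilution from a rate that will be reported.
- **The size is assumed.** The offsetting scenarios need a 30% or 50% fall in crises, 10 a year is the entry ceiling, and patients must be crisis-free for 4 weeks before randomization. This stands.
- **The table shells may already contain it.** SAP Section 2 puts the detailed table descriptions in a separate shell document, and the SAP's index of tables is not legible in the text reviewed. If a non-VOC row exists there, one sentence in SAP 7.2 settles the matter.
- **Leaving out VOCs could itself conceal harm.** SAP 8.2.1 counts acute chest syndrome, sequestration, priapism and all but clearly unrelated deaths as VOCs, and Protocol 3.8.8.6 allows that the drug might cause crises. This rules out basing the tolerability statement on a version without VOCs, or removing the subtypes from any version.

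**Conclusion.** The point holds as a gap in presentation. Crises enter the any-TEAE, frequency and severity components of the primary endpoint and the on-therapy SAE table. No table listed in SAP 7.2 gives the number of patients with at least 1 non-VOC TEAE, Grade ≥3 TEAE or SAE.

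Dilution of a patient-level risk difference to between 78% and 8% of its size follows from the 1-to-10 entry range only if past rates continue, events are Poisson, crises and other events are independent, and the drug does not affect crises. A vanishing or reversed difference further requires the drug to reduce crises. The documents support none of these as a forecast, so the true size is unknown.

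Two stronger readings are not supported. The primary endpoint as a whole is not compromised, because the drug-related component stands apart. SAE rates are not part of the primary endpoint in SAP Table 1. This is a cheap improvement worth making; no test, alpha level or sample size changes.

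**What to change.** In SAP 7.2:

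1. Keep all 12 current tables, with every event, as the main presentation.
2. Add supplementary versions of the overall TEAE summary, the TEAE severity table and the on-therapy SAE table that leave out events adjudicated as pain-crisis VOCs. Include in each the number of patients with at least 1 remaining event, and with at least 1 remaining Grade ≥3 TEAE in the severity version.
3. Keep deaths, acute chest syndrome, hepatic and splenic sequestration, and priapism in both versions.
4. State that adjudicated status decides what is left out, so that a reported crisis that adjudication did not confirm stays in. The AE tables otherwise rest on reported events, while SAP 8.2.1 uses adjudicated ones.
5. Read tolerability against placebo from both versions together with the two VOC tables (items 11 and 12).

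The cost is SAP wording and three extra descriptive tables, using the adjudication already planned in Protocol 5.13 and SAP 8.2.1. A drug-caused pain crisis would be absent from the supplementary version, but it stays visible in the main tables and the two VOC tables.

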### **7.3. Laboratory Evaluations**

Clinical laboratory parameters (chemistry, hematology, urinalysis) will be summarized as outlined in Table 7. Baseline is defined as the last non-missing measurement before administration of study treatment on Day 1 of the Double-blind Treatment Period. If there is more than 1 measurement for a laboratory parameter at a post-baseline time point, only the last measurement will be used. A listing of clinically significant clinical laboratory abnormalities will be presented. All lab data will be listed.

This document is confidential.

Table 7. Clinical Laboratory Summaries

Endpoint	Description	Timing	Summary Method
CTCAE v4.03 grading for laboratory values (Grades $\geq 3$ )	Summarized by laboratory parameter and CTCAE grade	First dose of study drug through last laboratory measure	Categorical summary
Descriptive	Summary of laboratory parameter (SI Units) at each timepoint measured plus change from baseline	Baseline, Week 1, Week 4, 8, 12 (EOT)	Continuous summary

CTCAE=Common Terminology Criteria for Adverse Events; SI=international system [of]; EOT=end of treatment.

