3. Patient is planning to undergo major surgery during the trial or has undergone surgery within 4 weeks of the Screening Visit, other than minor dermatologic procedures.

4. Patient has used oral or parenteral corticosteroids in the 8 weeks before the Randomization Visit. Note: Transient use for ≤ 2 days may be acceptable; consult the Medical Monitor for confirmation.
5. Patient has taken opioid(s) >200 morphine mg equivalent/day within the 4 weeks before the Randomization Visit.
6. Patient is taking aspirin ≥ 325 mg daily, any P2Y12 inhibitor, any anticoagulant medication, specific inhibitors of phosphodiesterase 5 (PDE5), nonspecific inhibitors of PDE5 (including dipyridamole and theophylline), any supplements for the treatment of erectile dysfunction, riociguat, or nitrates or nitric oxide donors in any form. These medications are prohibited from the Run-in Visit (which may occur from Day -14 to Day -17) through the duration of the study.

8. Patient has any of the following clinical laboratory values at the Screening Visit:
 - a. Hemoglobin ≤ 6 g/dL
 - b. Platelets $\leq 100 \times 10^9$ /L
 - c. Absolute neutrophils $\leq 1.5 \times 10^9$ /L
 - d. Alanine aminotransferase $>1.5 \times$ the upper limit of normal (ULN) as defined by laboratory
 - e. Direct bilirubin $>3 \times$ ULN as defined by laboratory
 - f. Creatinine clearance <30 mL/minute/1.73 m² by the Modification of Diet in Renal Disease equation (1):
$$\text{GFR (mL/minute/1.73 m}^2\text{)} = 175 \times S_{cr}^{-1.154} \times \text{Age}^{-0.203} \times 0.742 \text{ (if female)} \times 1.212 \text{ (if black)}$$
where S_{cr} is serum creatinine
 - g. Prothrombin time and/or activated partial thromboplastin time (aPTT) $>1.5 \times$ ULN and considered clinically significant by the Investigator, and/or international normalized ratio (INR) >1.5
8. Patient has oxygen saturation $\leq 90\%$ by pulse oximetry on room air at the Screening Visit and/or at the Randomization Visit.
9. Patient has had inpatient hospitalization for alcoholism or drug addiction in the 12 months before the Screening Visit or is positive for any the following at the Screening Visit unless legally prescribed:

Amphetamines	Benzodiazepines	Opiates	Propoxyphene
Barbiturates	Cocaine	Phencyclidine	

10. Patient has major concurrent illness or medical condition that in the opinion of the Investigator would preclude participation in a clinical study, including but not limited to:

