#### 7.4. Vital Signs

Vital signs (oxygen saturation, systolic and diastolic BP, orthostatic systolic and diastolic BP, pulse rate, orthostatic pulse rate, respiratory rate, and oral temperature) will be summarized as outlined in [Table 9](#). Based on the criteria in Table 8, the number and percentage of participants who had observed values and changes from baseline of clinical interest in vital sign parameters will be presented by treatment group.

Table 8. Criteria for Values of Clinical Interest in Vital Signs

Parameter	Flag	Criteria a	
		Observed Value	Change From Baseline b
Seated systolic blood pressure, mmHg	High	$\geq 180$	Increase of $\geq 10\%$ , $\geq 20\%$
	Low	$\leq 90$	Decrease of $\geq 10\%$ , $\geq 20\%$
Seated diastolic blood pressure, mmHg	High	$\geq 105$	Increase of $\geq 10\%$ , $\geq 20\%$
	Low	$\leq 50$	Decrease of $\geq 10\%$ , $\geq 20\%$
Seated pulse rate, bpm	High	$\geq 110$	Increase of $\geq 10\%$ , $\geq 20\%$
	Low	$\leq 50$	Decrease of $\geq 10\%$ , $\geq 20\%$
Seated O 2 saturation, %	High	NA	NA
	Low	<85%	NA
Oral temperature, C°	High	38°	NA
	Low	36°	NA
Respiratory rate, breaths per minute	High	18	NA
	Low	8	NA

NA=not applicable.

a A post baseline value is considered as clinical interest if it meets both the observed-value and the change-from-baseline criteria.

b Baseline is defined as the last non-missing measurement before administration of study treatment on Day 1 of the Double-blind Treatment Period

This document is confidential.

Table 9. Vital Signs Summaries

Endpoint	Description	Timing	Summary Method
Values of Clinical Interest Findings	Summarized by Vital Signs Measure. See Table 8 . (Participants meeting observed value criteria at Baseline are excluded.) 	First dose of study drug through last Vital Signs measure	Categorical summary
Descriptive	

Summary Vital Sign measures at each timepoint measured

Change from baseline in trough measurements

Change from predose to each postdose measurement at each visit (where applicable)

	Day 1, Week 1, Week 4, 8, 12 (EOT), F/U Visit	Continuous summary

EOT=end of treatment; F/U=follow-up

[1] Applies to Seated O2 saturation, oral temperature, and respiratory rate only.

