## 7.5. ECG 12-Lead Electrocardiogram (ECG)

12-lead ECG measurements will be performed at the scheduled time points, including the heart rate (HR), QT interval, RR interval, PR interval, or QTcF – Fridericia's Correction Formula. ECG overall result will also be collected on the electronic case report form (eCRF). If QTc result is outside of normal range, perform in triplicate and calculate the average. If ECG result is clinically abnormal, repeat.

This document is confidential.

Descriptive statistics for ECG parameters and changes from the baseline (Day 1) values at Week 1 and the end of treatment (EOT) visit will be presented by treatment group for the Safety Population. Change from predose to postdose for ECG parameters will also be calculated for the Day 1, Week 1, and EOT visits and summarized by treatment group. For ECG triplicates, the mean will be presented as the participant's value at a given visit.

The number and percentage of participants with absolute QTcF intervals in the following categories will be tabulated by treatment group: QTcF  $\leq$  450 ms, 450 ms  $<$  QTcF  $\leq$  480 ms, 480 ms  $<$  QTcF  $\leq$  500 ms, and QTcF  $>$  500 ms. Shift tables will be presented comparing values between baseline and Week 1 and EOT.

The number and percentage of participants with absolute HR in the following categories will be tabulated by treatment group:  $\leq$  50 bpm, 50 bpm  $<$  HR  $<$  110 bpm, and HR  $\geq$  110 bpm. Shift tables will be presented comparing values between baseline and Week 1 and EOT.

The number and percentage of participants with a change from baseline in QTcF interval according to the following categories will be examined: QTcF interval increases by more than 30 ms but not more than 60 ms, and QTcF interval increases by more than 60 ms.

Additionally, the number and percentages of participants with a change from baseline in HR according to the following categories will be examined: HR increases by more than 10 bpm but not more than 30 bpm, and HR increases by more than 30 bpm. Additionally, the number and percent of participants with a change from baseline in HR corresponding to a 20% increase or more will be calculated.

All ECG data will be listed. In addition, a listing of all AEs for participants with a QTcF increase of more than 30 ms or an HR increase of more than 30 bpm will be provided.

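### The Grade 3 or higher laboratory summary in SAP Table 7 takes no account of baseline grade, so persisting Day 1 abnormalities are counted together with new cases

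*SAP*

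**What the plan says.** SAP Section 7.3 summarizes laboratory parameters through the two rows of Table 7.

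- The categorical row covers CTCAE v4.03 Grade 3 or higher. It is "Summarized by laboratory parameter and CTCAE grade", over the window "First dose of study drug through last laboratory measure". It does not require worsening, exclude patients already at that grade, or cross-classify by baseline grade.
- The continuous row is a "Summary of laboratory parameter (SI Units) at each timepoint measured plus change from baseline".

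The same section defines baseline: "Baseline is defined as the last non-missing measurement before administration of study treatment on Day 1 of the Double-blind Treatment Period". Only the continuous row uses it. Protocol Section 5.9.1 plans descriptive values and changes from baseline, with no graded or shift display.

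Elsewhere the SAP does bring baseline into its categorical safety summaries. For blood pressure and pulse, a footnote to Table 8 states: "A post baseline value is considered as clinical interest if it meets both the observed-value and the change-from-baseline criteria". For oxygen saturation, temperature and respiratory rate, where no change criterion is set, Table 9 states: "Participants meeting observed value criteria at Baseline are excluded". For QTcF and heart rate categories, Section 7.5 states: "Shift tables will be presented comparing values between baseline and Week 1 and EOT".

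**The concern.** A count of Grade 3 or higher values after first dose is informative about the drug only if the reader can separate values that became severe from values that were severe already. Followed as written, Table 7 mixes the two.

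Sickle cell disease is described in Protocol Section 1.1 as a hemolytic condition, so abnormal hematology and bilirubin at entry are plausible. The arms are small. A chance difference in the number of patients entering at Grade 3 or higher would carry into the table and could look like a drug effect or offset one. Even with balanced arms, a common block of carried-over cases pulls the ratio of the two rates toward 1. Safety is the primary objective, so a table of severe laboratory values will be read closely although it is only descriptive.

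**Working it through.** The plan states no figure on this point, so there is none to reproduce. The check is a reading of the entry rules followed by an illustration under stated assumptions.

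**Can patients be at Grade 3 or higher on Day 1?** The exclusion criterion on laboratory values reads "Patient has any of the following clinical laboratory values at the Screening Visit". Its limits are absolute values or multiples of the ULN, not CTCAE grades. They cover hemoglobin, platelets, neutrophils, ALT, direct bilirubin, creatinine clearance and coagulation. Protocol Table 4 also lists total and indirect bilirubin, AST, GGT and lymphocytes, which have no limit. The Schedule of Events allows Screening as early as Day -43. It reconfirms eligibility on Day 1, but the laboratory criterion refers to Screening values only, whereas the oxygen saturation criterion names both Screening and Randomization. So the documents do not rule such patients out. They contain neither the CTCAE cut-offs nor an expected baseline share.

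**Arm sizes.** Amendment 4 onward: about 48 at 3:1 gives 48 × 3/4 = 36 on 18 mg and 48/4 = 12 on placebo (PBO2). Amendment 3 or earlier: about 40 at 1:1:1:1 gives 10 on placebo (PBO1). Overall placebo is 10 + 12 = 22.

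**Chance imbalance.** Let p be the share at Grade 3 or higher at baseline, with every such value persisting. The SD of the arm difference from this source is √[p(1−p)(1/n₁ + 1/n₂)].

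| Comparison | 1/n₁ + 1/n₂ | p = 10% | p = 40% |
|---|---|---|---|
| 36 vs 12 | 0.1111 | √(0.09 × 0.1111) = 10.0 points | √(0.24 × 0.1111) = 16.3 points |
| 36 vs 22 | 0.0732 | √(0.09 × 0.0732) = 8.1 points | √(0.24 × 0.0732) = 13.3 points |

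At these shares, the expected carried-over counts are 3.6 to 14.4 of 36 and 1.2 to 4.8 of 12. Exact binomial enumeration for 36 vs 12 gives a probability of 33%, 47% and 53% that the baseline shares differ by at least 10 points, at p = 10%, 20% and 30%.

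**Dilution.** Let s be the proportion of baseline cases that persist and r the rate of new cases among the rest. The counted rate is p·s + (1−p)·r. Assume s = 90%, with r = 15% on active and 5% on placebo, a true ratio of 3.0.

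| p | Active | Placebo | Ratio |
|---|---|---|---|
| 10% | 0.090 + 0.135 = 22.5% | 0.090 + 0.045 = 13.5% | 1.67 |
| 20% | 0.180 + 0.120 = 30.0% | 0.180 + 0.040 = 22.0% | 1.36 |
| 30% | 0.270 + 0.105 = 37.5% | 0.270 + 0.035 = 30.5% | 1.23 |

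The absolute difference shrinks less, from 10 points to 9, 8 and 7.

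**Effect of a baseline rule on the count.** With p = 20%, s = 90% and r = 5%, the 18 mg arm shows 36 × 0.22 = 7.9 patients as written. If only patients below Grade 3 at baseline could count, it would show 36 × 0.80 × 0.05 = 1.4.

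**The case against.** Much of the case on the other side stands.

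- **Primary safety result.** A reader might infer that baseline abnormality is reported as on-treatment toxicity and enters the primary safety result. The documents do not support that. Table 7 is not labelled toxicity or treatment-emergent, and its window is not limited to treatment. The TEAE tables use an onset rule (SAP Section 5.2.4). Protocol Section 3.8.8.7 treats a condition present at screening that does not worsen as medical history.
- **Share of carried-over cases.** A reader might infer that, in an anemic population, the table would mostly show who was abnormal on entry. That depends on an unknown share. With s = 90%, p = 5% and r = 10%, carried-over cases are 0.045/(0.045 + 0.095) = 32% of the count; with p = 20% and r = 5% they are 0.18/0.22 = 82%. Several entry limits (platelets, neutrophils, ALT, INR) also restrict who can enter with abnormal values.
- **Other analyses.** Hemoglobin has a baseline-adjusted ANCOVA and an MMRM (SAP Sections 8.3.1 and 8.3.2). Change from baseline is also summarized for LDH, reticulocytes, bilirubin, haptoglobin and cystatin C. A hidden effect on these markers is unlikely to rest on Table 7 alone.
- **Noise.** Small arms are noisy whatever the rule: a table of new cases only, at a 5% rate, has an SD of √(0.05 × 0.95 × 0.1111) = 7 points for 36 vs 12.
- **Consistency.** The orthostatic counts in SAP Section 7.4 carry no baseline rule either, so laboratory grades are not the only exception.
- **Unseen material.** The TFL shells and the index of tables cannot be seen and might contain a baseline column.

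These points limit the size of the concern. They do not remove it. Section 7.3 defines the summary by the text of Table 7, and that text has no baseline rule. Mean changes and listings let a reader look further but do not correct the categorical count.

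**Conclusion.** The point holds for one descriptive table. As written, a patient at Grade 3 or higher on Day 1 who stays there is counted in Table 7 with no way to tell that case from a new one. The entry rules do not exclude such patients, but their number is not given, so the size is conditional. For an assumed baseline share of 10% to 40% with persistence, the SD on the arm difference is about 10 to 16 points against PBO2 and 8 to 13 points against overall placebo. A true threefold ratio in new cases would appear as 1.67 to 1.23 at shares of 10% to 30% with 90% persistence. If few patients enter at Grade 3 or higher, or their values improve, the effect is smaller. The primary TEAE analysis, the change-from-baseline summaries and the hemoglobin models are unaffected, and no formal test is distorted because safety is analyzed descriptively. This is a minor-to-moderate weakness.

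**What to change.** In SAP Table 7, define the categorical row as Grade 3 or higher values that are worse than the patient's baseline grade, using the baseline already defined in Section 7.3. Add a shift table from baseline grade to worst post-baseline grade, by parameter and treatment arm. State also that first dose means the first randomized dose, because SAP Section 4.2 uses the term study drug for the run-in placebo as well.

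The cost is a few lines of SAP text, one added table shell and its programming. Laboratory blood samples are already drawn predose on Day 1, so no new data, visits or patients are needed.
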